**Participant randomization.** Upon completing baseline questionnaires, a computer-generated, blocked randomization scheme in the REVAMP program will automatically allocate eligible participants into one of two groups: *REVAMP management versus in-person management*. Randomization at each site will be programmed by SAS module Proc Plan. Block size at each site will be six subjects so that among each block of six randomized individuals, exactly three will be assigned to each group in a random order. Investigation and management of the two arms of care will be conducted over equal time periods.

**REVAMP pathway.** Following completion of the website questionnaires and the HST, REVAMP participants will be scheduled for an initial phone interview with the *sleep specialist (MD or NP)* (Fig 4). The practitioner will review the results with the subject. *Using the criteria required by the Center of Medicare and Medicaid Services, participants with AHI  $\geq 15$  events/hr and subjects with  $5 \leq AHI < 15$  who have OSA-related symptoms will be diagnosed with OSA.* Those interested in PAP treatment will be prescribed an APAP unit with wireless modem. Subjects with OSA who are found on follow-up to require bilevel PAP and/or supplemental oxygen will continue to participate in Aim 1. Participants testing negative for OSA will be offered usual clinical care to further evaluate their sleep-related symptoms. Participants with a diagnosis of central sleep apnea/Cheyne-Stokes respiration

(CSA/CSR) will be referred to a sleep physician and PSG testing. *Participants without OSA on HST and participants with CSA/ CSR will not be included in the Aim 1 modified intent to treat analysis set but will be included in the primary analysis set of Aim 2 and Aim 3.*

The wireless modem on the home PAP unit sends PAP data daily to the manufacturer's server which in turn exports the data daily to the REVAMP website. The website displays the following information in an easily understandable format: hours of use, amount of air leak, and AHI (Fig. 2). Participants and practitioners can view the data on the REVAMP website. Participants will be instructed to review their results on the website daily. The number of times a subject logs into the website will be tracked.

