Following the first week of PAP treatment, a therapist with at least one year of experience managing patients with OSA will phone the participant. Using a standardized protocol, the therapist will evaluate the participant's response to treatment, inquire if any barriers are limiting PAP use, and provide advice on how to overcome those problems (see *Appendix 4*). The therapist will encourage the participant to review his/her PAP data on the website. The participant will be scheduled for 1- and 3-month follow-up phone calls with the therapist. Additional phone calls are allowed as clinically indicated and will be tracked. The therapist will have the option of consulting with the sleep specialist (MD or NP). Upon consultation, if it is felt that the problem cannot be addressed by phone, the participant will be scheduled for an in-person clinic appointment with the physician. The type, number

and duration of all encounters will be recorded in case report forms. All phone clinic sessions and other patient encounters will be documented in the participant's electronic medical record.

REVAMP has a secure message system that sends e-mail and text messages to the participant alerting him/her to login to the website to view a message. The REVAMP website will use this feature to remind the participant to complete questionnaires, view their PAP data, and keep scheduled phone clinic appointments.

*In-person management.* Participants in the in-person arm will be scheduled to meet with the sleep therapist for in-person set-up instructions for HST. Following HST, a sleep specialist (MD or NP) will conduct the initial in-person clinic evaluation. Participants diagnosed with OSA (using the same criteria detailed above for the REVAMP pathway) who are willing to start PAP treatment will be prescribed APAP. Sleep therapists with at least one year of experience managing patients with OSA will perform the follow-up clinic evaluations. Participants will receive a 1-week phone call and be scheduled for 1- and 3-month in-person follow-up clinic visits. Additional phone calls and clinic visits will be allowed as clinically indicated. The type, number and duration of all encounters will be monitored and documented in the participant's electronic medical record.

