**Modified intent-to-treat and per-protocol populations.** Primary analysis for non-inferiority will be based on all randomized participants initiated on APAP with at least one FOSQ follow-up score. In a secondary analysis, the non-inferiority test will be repeated using a per protocol cohort (patients who have been initiated on APAP and have non-missing endpoints at month 3), since protocol violations can add noise making it more difficult to distinguish between the two active treatment groups.

**Statistical methods for Aim 2.** Aim 2 will determine if REVAMP management of patients with OSA is cost-effective compared with in-person care. The perspective of the analysis will be that of the VA. While the VA has the general well-being of veterans as its goal, we will focus our attention on health care costs, in part because VHA patients with OSA are older and less likely to work. The analyses for Aim 2 will be based on all randomized participants, as this is the target population for the evaluation of Aim 2 and Aim 3 outcomes related to management of this patient population. We will perform a secondary analysis using the modified intention to treat sample (Aim 1 analysis set). The primary outcome measure in Aim 2 will be the difference in sleep-related cost between the two delivery modalities. Our hypothesis is 2a)  $H_0: \Delta C = 0$  vs  $H_A: \Delta C < 0$ . Based on data from our prior study of home vs in-lab diagnosis, we assume average 3-month sleep-related costs of \$1755 (SD, 745) for the home group and of \$2538 (SD, 1065) for the in-lab group. Resulting power is 1.0 for sample size of 114 per group and remains greater than 0.9 if, when including participants without OSA on HST and participants with CSA/CSR, the means are reduced by 25% and the SDs are increased by 25%.

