Secondary outcome measures include the difference in total costs, the difference in QALYs, and the ratios of the differences in cost and QALYs. The secondary hypothesis for the cost-effectiveness ratio is 2b)  $H_0: \Delta C/\Delta Q > 100,000$  vs  $H_A: \Delta C/\Delta Q \leq 100,000$ . As with the efficacy and non-inferiority analyses, the cost difference ( $\Delta C$ ) and the preference score difference ( $\Delta Q$ ) will be estimated using mixed effect models for longitudinal data. QALYs will be constructed by taking the area under the quality-adjusted survival curve. The cost-effectiveness ratio ( $\Delta C/\Delta Q$ ) will be calculated by dividing the estimated difference in cost by the estimated difference in QALYs. Confidence intervals for the cost-effectiveness ratios will be calculated using Fieller's theorem method. A point estimate less than 100,000/QALY and a 90% confidence interval that excludes \$100,000 will be evidence that we can reject the null hypothesis that the incremental cost-effectiveness ratio is not less than \$100,000.

Costs, QALYs, and cost-effectiveness ratios will be calculated for costs and effects during the first 3 months following initiation of APAP treatment and for the full period of follow-up (maximum, 2 years). The study design (follow-up extending from enrollment until 3 months after last patient is enrolled) introduces substantial administrative censoring that – as with the primary analysis – will be addressed by use of a mixed model approach (i.e., patients will have different lengths of follow-up, and thus different costs and QALYs, simply because they were enrolled at different times). Because this censoring is due primarily to administrative reasons, it is generally considered to yield data that are missing completely at random (MCAR). While use of the electronic medical records for the collection of cost data will lead to limited missing cost data, there may be censoring of cost data for services outside the VHA and of the QALY measures due to loss to follow-up. If such drop-out is related to disease severity or to outcomes after randomization, it generally would be considered to yield data that are either missing at random (MAR) or that are non-ignorably missing.

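### The short-term Aim 2 window starts at APAP initiation, a date about 71 of the 356 randomized participants would not have, and no window is designated for primary hypothesis 2a

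*Combined protocol and SAP*

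**What the plan says.** **Population.** Statistical methods for Aim 2 states: "The analyses for Aim 2 will be based on all randomized participants". The REVAMP pathway section adds that participants without OSA on home sleep testing (HST), and those with central sleep apnea or Cheyne-Stokes respiration (CSA/CSR), "will be included in the primary analysis set of Aim 2 and Aim 3". The mITT set, limited to participants started on APAP, is used for a secondary Aim 2 analysis.

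**Windows.** The same Aim 2 section calculates costs, QALYs and ratios for "costs and effects during the first 3 months following initiation of APAP treatment and for the full period of follow-up (maximum, 2 years". Full follow-up is described there as beginning at enrollment.

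**Who starts APAP.** Randomization follows the baseline questionnaires and precedes sleep testing. After diagnosis, "Those interested in PAP treatment will be prescribed an APAP unit with wireless modem". Participants who test negative are offered usual care.

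**Hypothesis 2a.** The Aim 2 primary outcome is the between-arm difference in sleep-related cost, with no period attached. The power statement reads "we assume average 3-month sleep-related costs of" $1755 (SD 745) and $2538 (SD 1065). A second scenario applies "when including participants without OSA on HST and participants with CSA/CSR, the means are reduced by 25" percent and the SDs raised by the same percentage.

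**The concern.** A window needs a time zero that every member of the analysis set has. APAP initiation happens after randomization and depends on both diagnosis and willingness to be treated, so part of the stated Aim 2 population cannot be placed in the short-term window. An analyst would have to improvise: drop these participants, count them as zero cost, or assign a nominal date. These choices estimate different quantities, and the plan selects none of them.

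The anchor also falls late in the care pathway. By the time APAP starts, participants have already been through HST set-up and the initial evaluation, two steps at which web-based and in-person care differ. A short-term cost comparison of the two pathways that begins afterwards does not cover the whole difference between them.

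For 2a, the only 3-month cost window with a defined start is the APAP-anchored one. If 2a is meant to use it, the problem reaches the Aim 2 primary test. If not, its start date remains to be settled, possibly after results are known.

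**Working it through.** **1. Reproduce the enrollment figure.** Inputs from Sample size, and power: 114 per group, 20% without OSA, 20% drop-out after APAP start.
- 2 × 114 = 228; 228 / (0.80 × 0.80) = 356.25, matching the stated 356.
- The calculation makes no separate allowance for OSA participants who decline PAP.

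**2. Participants with no start date.**
- Without OSA: 0.20 × 356 = 71.2, about 71 (about 36 per arm). With OSA: 356 − 71.2 = 284.8.
- PAP decliners: no rate is given. Assuming 0% to 10% of 284.8 adds 0 to 28.5, for a total of 71 to about 100 (20% to 28% of 356).
- Whether the 20% covers CSA/CSR is not stated. These are shares of people, not of cost.

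**3. What the window leaves out.**
- In-person arm: "Participants in the in-person arm will be scheduled to meet with the sleep therapist for in-person set-up instructions for HST". Then: "Following HST, a sleep specialist (MD or NP) will conduct the initial in-person clinic evaluation".
- REVAMP arm: the monitor is supplied without in-person instruction (Home sleep testing and polysomnogram), and the first specialist contact, also after HST, is by phone (REVAMP pathway).
- Table 2 puts the initial assessment at Week 2-4, APAP set-up at Week 8 and the 3-month follow-up at Week 20. On that schedule the short-term window covers Weeks 8 to 20 and excludes Weeks 0 to 8.
- No cost is given for the excluded steps, so no bias can be calculated.

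**4. Check the 2a power statement.** Normal approximation, 114 per arm; one-sided 0.05 and 0.025 are both tried because no alpha is stated for 2a.
- Base case: difference 2538 − 1755 = 783; SE = √((745² + 1065²)/114) = 121.7; power about 1.0, as stated.
- Second scenario: difference 0.75 × 783 = 587; SE = 1.25 × 121.7 = 152.2; power 0.99 (0.05) or 0.97 (0.025), consistent with the stated figure above 0.9.
- All randomized, 178 per arm, second-scenario inputs: power 0.999 or 0.998.

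The power figures hold. The gap concerns what is estimated, not whether the sample is large enough.

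**5. Look for a substitute date.** The mixed model in the Aim 2 section deals with censoring and does not define a start. Table 2 is headed for all participants and gives nominal weeks, but the text does not use Week 8 as a default start for non-starters.

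**The case against.** Several points on the other side stand.

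- **Restriction to APAP starters.** A reader might infer that the plan limits the short-term analysis to them. It does not say so, and its population statement says the opposite. Restriction is one literal way to resolve the conflict, and would give a set close to the mITT set.
- **No horizon for 2a.** A reader might infer that the period for 2a is wholly open. The power statement implies 3 months, and its second scenario shows that participants without OSA were expected to contribute costs. What is missing is a start date and a formal designation. The available text opens at Research Design and Methods, so a statement of the hypotheses elsewhere might supply one.
- **Biased cost result.** This cannot be shown. For the 71, OSA status largely predates randomization, the diagnostic criteria are the same in both arms, and the interpreting specialist is blinded to arm. PAP decliners are the more arm-sensitive group, and their number is unknown.
- **Lost diagnostic costs.** They are not lost. The Aim 2 measures section tracks diagnostic and PAP costs and collects service use from enrollment onward, and the full-follow-up analysis includes them.

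None of this gives non-starters a time zero or brings the diagnostic steps into the short-term window.

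**Conclusion.** The concern holds as a conflict of definitions. The short-term Aim 2 window cannot be applied to the population the plan assigns to it. About 71 of 356 participants (20%) have no start date on the plan's own figure, rising to about 100 (28%) if 10% of those with OSA declined PAP, which is an assumption. Some participants negative on HST might start APAP after a later polysomnogram, so 71 is a planning figure, not an exact count. For everyone who can be placed in the window, it omits two pre-APAP steps that differ by arm. In the available text, 2a has an implied 3-month horizon but no designated window.

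Aim 1, the power calculations, data collection and the full-follow-up analysis are untouched. The point should be fixed before analysis because it could reach the Aim 2 primary test.

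**What to change.** 1. Start the short-term Aim 2 window at randomization for every participant, whatever the diagnosis or PAP uptake, with one fixed length in both arms.
2. State in advance which window tests 2a.
3. Keep the 3-month APAP-anchored window for the secondary mITT analysis.
4. Calculate QALYs to the fixed end date as area under the curve, interpolating between actual measurement dates. Starters' 1- and 3-month questionnaires are timed from treatment initiation (Sample size, and power; Missing data methods), so Table 2's Week 20 coincides with a measurement only if set-up occurs at Week 8.
5. State when non-starters complete their questionnaires.

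The length needs thought. On Table 2's schedule, 3 months (about 13 weeks) from randomization would contain only about 5 weeks of APAP (13 − 8), whereas 20 weeks would reach the nominal 3-month follow-up.

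**Cost.** SAP wording and a clarification of questionnaire timing; no new cost data, since costs are already collected from enrollment. Two downsides: arm differences in time to APAP start push some treatment cost and QALYs outside a fixed window, and QALYs at its end require interpolation. The APAP-anchored mITT analysis can show the first.

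The conflict over when follow-up ends (at least 9 months of post-treatment cost data in Sample size, and power; 3 months after the last enrollment in Statistical methods for Aim 2) is a separate matter and should be raised on its own.

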All participants will complete the website questionnaires in order to standardize collection of our functional outcomes. Practitioners in both arms will not have access to the responses to the patient satisfaction questionnaires (WAI-SR and CSQ-8). The other questionnaire responses of the participants randomized to REVAMP management will be available to the practitioners performing the phone clinic evaluations. Enrolled subjects assigned to the in-person arm will only have access to the website's questionnaires but none of its other features. They will be informed that a research staff member will contact them to schedule their first clinic appointment. None of the questionnaires they complete on the website will be shared with their practitioners. At the time of their in-person clinic visits, these participants will complete the questionnaires that are routinely used as a part of the clinical site's usual care. That information will not be collected for analysis.

**Table 2.** Data collection and action schedule for all participants

Measures & Procedures	Baseline assessment	Initial clinical assessment	AutoCPAP set-up	1-week phone FU	1-month FU assessment	3-month FU assessment
	Week 0	Week 2-4	Week 8	Week 9-12	Week 12	Week 20
Eligibility criteria	In-person					
Informed consent	In-person					
Patient characteristic questionnaire	website					
Functional & QOL questionnaires†	website				website	Website Δ
Therapy process indicators‡		website		website	website	Website Δ
Clinical assessment*		In-person vs phone		Phone	In-person vs phone	In-person vs phone
APAP set-up			DME			
APAP adherence*				Wireless	Wireless	Wireless

DME = home health care company; FU=follow-up; QO =quality of life; Δ=performed every 3 months thereafter to the end of data collection

\* Subjects randomized to in-person management will have in-person clinic evaluations in the sleep center and subjects randomized to REVAMP management will have phone clinic sessions. APAP adherence in both groups will be obtained by wireless modem.

[figure not shown]
† Functional & QOL questionnaires: FOSQ-10, ESS, SF-12, CES-D, and EQ-5D; ‡ Therapy process indicators: WAI, CSQ-8 (performed within 1-week following each encounter)

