*Scoring of sleep testing.* The HSTs and PSGs will be scored by an experienced PSG technologist at the respective clinical site and interpreted by a sleep specialist at that site who is blinded to randomization arm and not involved with participant management. The decision not to have centralized scoring of the sleep tests increases the "real world" nature of the project, improves turn-around time, and reduces project cost. On both HST and PSG, events with at least a 30% reduction in respiration for at least 10 sec associated with a 4% or greater oxygen desaturation will be scored as hypopneas. A recent study by the PI that compared scoring of PSGs at 5 sleep centers found an interclass correlation coefficient for AHI of 0.98 using these scoring criteria. To standardize scoring procedures at the sites, a manual that details scoring procedures will be developed. AHI will be calculated as the average number of apneas and hypopneas per hour of sleep on PSG and as the average number of those events per hour of recording on HST.

*Long-term follow-up.* Following the 3-month follow-up, participants will be scheduled for a follow-up with the sleep therapist every 6 months for the duration of their participation. Participants in the in-person arm will have in-person clinic appointments. Participants in the REVAMP arm will have phone clinic sessions.

*Controlling patient wait time.* We will monitor patient wait time throughout the protocol to compare the efficiency of REVAMP versus in-person management. REVAMP management will have a fixed schedule as detailed above. In order to match this timeframe, we will set a maximum limit to wait times for participants in the in-person group. Wait time for current in-person care varies widely across sleep centers. In order to enhance the applicability of our results to other sleep centers in the VHA and private sector, we will limit wait times of subjects in the in-person arm so that the initial clinic visit and sleep testing occur within one month of enrollment and the first follow-up clinic visit occurs within the first month of PAP treatment. This represents the current practice of

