### Aim 2 - Measures to be used in cost, utility, and cost-effective analysis (see Appendix 3 for questionnaires)

Medical service use and costs, stratified by whether or not they are related to the diagnosis and treatment of OSA, will be collected for the 6 months prior to enrollment and the entire observation period following enrollment. We will track the cost of all tests, treatments, and equipment (for diagnosis, PAP). Starting in the third quarter of the study (equivalent to the beginning of the second quarter of enrollment) and continuing quarterly for a total of 6 quarters, providers will be asked in the second week of the quarter to report the time they spent managing individual participants during the prior week. Obtaining measurements for a week reduces problems of recall; obtaining them over a year allows capture of changes in physician time that may occur over the study period. The cost of participant travel time will be based on the distance the participant lives from the sleep center. Participants will be asked to recall the time they spent performing activities related to sleep services during their one- and three-month follow-up interviews. We will also collect all costs pertaining to non-OSA sleep-related disorders.

Medical service use and cost data incurred within the VHA will be obtained through access to the Managerial Cost Accounting (MCA) System at the Corporate Data Warehouse (CDW), the VA national data repository. MCA National Data Extracts (NDEs) data originate from various site-level MCA databases and subsystems at the patient level. We will select NDEs to obtain in-patient, outpatient, laboratory, pharmacy, radiology, and surgery services provided to each participant and their associated cost. To gain research access to MCA data, a Data Access Request Tracker (DART) application will be submitted to the National Data Systems (NDS). Once approved for access, the requested information, typically in the format of SQL server output tables, will be provided by the VA Informatics and Computing Infrastructure (VINCI). Fee-based non-VA care on the CDW will be requested from VINCI. Cost and use of Centers for Medicare and Medicaid Services (CMS) by participants

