Based on current referrals to the 3 clinical sleep centers, we anticipate that 20% of subjects enrolled will not have OSA. Adding to this estimate a 20% drop-out rate of patients diagnosed with OSA and initiated on APAP, we need to enroll a total of 356 subjects, i.e., approximately 119 subjects per clinical site. We are confident that we will be able to achieve this goal. Given our clinic and personnel resources, we plan to enroll 6 patients per month per site. We anticipate that it will take about 2 years to enroll the participants (see Gant chart). Thus, we will have at least 9 months of post treatment cost data on all participants for our cost-effectiveness analysis, while the longest will be about 2 years. The longer follow-up should provide the opportunity to observe potential long-term cost benefit and outcome differences between the testing methods.

**Descriptive comparisons at baseline.** Descriptive statistics will be computed for all outcomes; distribution checks will be performed using histograms, quantile plots, and goodness-of-fit tests. Sample characteristics will be summarized using mean (SD) for continuous outcomes and frequency and percent for categorical variables. Descriptive analyses will be performed to characterize the treatment groups separately by clinical center and to confirm that the randomization resulted in no clinically significant treatment group differences at baseline. Partial correlations (controlling for site and group) between baseline factors and outcome measures will be computed to identify potentially important covariates. The primary non-inferiority tests will be repeated, controlling for baseline factors that are found to have both clinically significant treatment group differences and evidence of association with either 1-month or 3-month change in FOSQ score.

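### The promised minimum of 9 months of post-treatment cost data disagrees with the Aim 2 rule that ends follow-up 3 months after the last enrollment

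*Combined protocol and SAP*

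**What the plan says.** Three parts of the combined protocol and SAP bear on how long participants are followed.

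- **Statistical analysis, sample size and power.** After the enrollment target of 356 and an accrual time of about 2 years, the text states that "we will have at least 9 months of post treatment cost data on all participants", with the longest follow-up about 2 years. The accrual timing refers to a timeline chart that is not in the supplied text.
- **Statistical methods for Aim 2.** The design is described as "follow-up extending from enrollment until 3 months after last patient is enrolled". This rule is given as the source of substantial administrative censoring, and the differing lengths of follow-up are said to produce differing costs and QALYs. Results are planned for the first 3 months of APAP and for the full follow-up, with a 2-year maximum.
- **Schedule and measures.** Table 2 places APAP set-up at Week 8 and the 3-month assessment at Week 20. Its footnote has questionnaires "performed every 3 months thereafter to the end of data collection", without defining that end. The Aim 2 measures section collects costs for the 6 months before enrollment and for "the entire observation period following enrollment".

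**The concern.** One sentence sets a floor of 9 months after treatment for everyone. The other closes follow-up 3 months after the last person joins. Because treatment starts some weeks after enrollment, a 3-month close-out cannot give the last enrollees 9 months of treated time.

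The close-out date determines how much data the full-period Aim 2 analysis has. After month 3 the arms still differ in delivery: the long-term follow-up section says that "participants will be scheduled for a follow-up with the sleep therapist every 6 months for the duration of their participation", in person in one arm and by phone in the other. A reader judging how well the trial can observe longer-term cost differences would reach different views from the two sentences. If the Aim 2 wording were also applied literally as a data cut, some late enrollees would close before their 3-month assessment.

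**Working it through.** **Inputs.** 356 enrolled; 6 per month at each of 3 sites, so 18 per month; accrual of about 2 years (sample-size text). Set-up at Week 8, 3-month assessment at Week 20 (Table 2). Close-out 3 months after the last enrollment (Aim 2 methods).

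**Assumptions.** Uniform accrual; one month = 52/12 weeks; 3 months = 13 weeks and 9 months = 39 weeks, with a variant of 12 and 36 weeks because Table 2 spaces set-up and the 3-month assessment 12 weeks apart.

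**The plan's own figures.** Enrollment reproduces: 2 × 114 / (0.80 × 0.80) = 356. Accrual is 356/18 = 19.8 months (85.7 weeks) at the planned rate, or 24 months (104 weeks) as stated. The 9-month minimum does not reproduce from the Aim 2 rule, as follows.

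**Minimum follow-up after set-up** = close-out week of the last enrollee − 8.

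- Close-out at the end of the last participant's 3-month assessment: 8 + 13 = Week 21, so 13 weeks (Week 20 and 12 weeks in the variant). That is 3 months.
- Literal reading: Week 13, so 13 − 8 = 5 weeks.
- Needed for 9 months: 8 + 39 = Week 47, or 10.8 months after the last enrollment (Week 44 in the variant).

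**Share short of 9 months** = (needed week − close-out week) / accrual weeks.

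| Reading | Gap | 24-month accrual | 19.8-month accrual |
|---|---|---|---|
| 3-month assessment, 12-week quarters | 44 − 20 = 24 wk | 23% (82 of 356) | 28% (100) |
| 3-month assessment, 13-week quarters | 47 − 21 = 26 wk | 25% (89) | 30% (108) |
| Literal | 47 − 13 = 34 wk | 33% (116) | 40% (141) |

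**Closing before Week 20, literal reading only:** 20 − 13 = 7 weeks; 7/104 × 356 = 24 and 7/85.7 × 356 = 29, or 7-8%. On the other reading, none.

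**Which sentence fits the stated longest follow-up of about 2 years?** Longest = minimum + accrual.

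- 9-month minimum: 9 + 19.8 = 28.8 to 9 + 24 = 33 months.
- 3-month minimum: 22.8 to 27 months.
- Literal (5 weeks = 1.15 months): 20.9 to 25.2 months.

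The shorter close-out fits better unless 2 years is a cap on the analysis.

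**Aim 2 power check.** The plan says "Resulting power is 1.0 for sample size of 114 per group and remains greater than 0.9" with means reduced by 25% and SDs increased by 25%; the cost assumptions are for 3 months. Suppose the literal cut cost 29 enrollees: 29 × 0.80 × 0.80 / 2 ≈ 9 per group, leaving 105. The difference is 0.75 × (2538 − 1755) = 587.25 and the SDs are 931.25 and 1331.25. The standard error is √[(931.25² + 1331.25²)/105] ≈ 158.5 and z ≈ 3.70. By the normal approximation at alpha 0.05, power is about 0.98 one-sided and 0.96 two-sided, still above 0.9.

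**The case against.** **The literal reading is unlikely.** Table 2 applies to all participants and the primary outcome is measured 3 months after APAP starts, so the Aim 2 sentence is probably loose wording for the end of the last 3-month assessment. This stands. It is why the 23-30% range should lead and the literal counts come second. It does not restore 9 months.

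**Cost data could be extracted later.** VA costs come from records, so 9 months of cost data might be pulled after participant follow-up ends. This does not stand on the text. The Aim 2 methods tie length of follow-up to costs, and the measures section limits costs to the observation period. Adding the 6 months before enrollment to 3 months after it does not help either, since the promise is of post-treatment data.

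**The consequences are limited.** The 9 months is a forecast, administrative censoring is acknowledged, and the mixed model allows for unequal follow-up. This stands and holds the severity down. The model does not say which minimum applies.

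**Stronger readings to avoid.** A reader might infer that participants without 9 months contribute nothing to the later cost comparison. They still contribute clinically indicated contacts, equipment, other services and quarterly questionnaires. A reader might also infer that the primary FOSQ-10 analysis or the Aim 2 power is undermined. The first would be touched only under a literal data cut, for 7-8% of enrollees, and the power claim survives even then. Nor do the documents show that no close-out date was set, because the cited chart was not available.

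**Conclusion.** The inconsistency is real and minor. Neither the literal rule nor its more plausible reading delivers the stated 9-month minimum. On the more plausible reading the true minimum is about 3 months and roughly a quarter of enrollees fall short of 9. The percentages rest on uniform accrual and on set-up occurring at Week 8 as scheduled. The longest follow-up of about 2 years suggests that the 9-month figure is the one out of line, but without the timeline chart this is not settled. What is at stake is chiefly the amount of later data behind the full-period costs, QALYs and cost-effectiveness ratio, which are secondary.

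**What to change.** State one close-out rule, no earlier than the last participant's Week 20 assessment, and define the end of data collection in the Table 2 footnote by it. Give the resulting minimum follow-up in the same words in the sample-size text and the Aim 2 methods, correcting the 9-month figure if it is not kept. Say whether 2 years is an analysis cap and from what date it runs.

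Most of this is wording. Securing Week 20 adds at most about 7 weeks (20 − 13) of web questionnaires and modem data for the last enrollees, and nothing if that was already intended. Keeping 9 months adds about 24-26 weeks beyond the last 3-month assessment, or 34 weeks beyond the literal close-out. For VA costs that is mainly a later records pull; for questionnaires and self-reported outside care it is longer web follow-up. If 9 months is dropped, the price is a less favorable stated minimum.
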